  - b. Patients who submitted transurethral resection of bladder tumor (TURBT) specimens are required to submit specimens containing muscle invasive component of the bladder tumor as verified by pathology review. If the TURBT specimens do not contain a muscle invasive component (i.e., T2 or greater), then specimens obtained at the time of cystectomy/nephroureterectomy or metastatic spread (i.e., sample from a metastatic lesion) are required. An archival specimen, if available, must also be submitted.
  - c. Patients who do not have tissue specimens meeting eligibility requirements must undergo a biopsy sample collection during the screening period. Acceptable samples include core needle biopsies for deep tumor tissue (resulting in ten 4 $\mu$ m and one 20 $\mu$ m slides of evaluable quality) or excisional, incisional, punch, or forceps biopsy samples for cutaneous, subcutaneous, or mucosal lesions.
  - d. Patients having additional tissue samples from procedures performed at different times during the course of their urothelial carcinoma are requested (but not required) to also submit these samples for central testing. In situations where multiple specimens are received from different sites or at

different times, the highest score will be used for primary and secondary analyses.

- Inclusion for Cohort 1
9. Untreated with chemotherapy for metastatic disease
  10. Have at least one of the following:
    - a. ECOG (Eastern Cooperative Oncology Group) performance status of 2.
    - b. Glomerular filtration rate calculated as creatinine clearance (Cockcroft-Gault formula) of  $\geq 20$  mL/min and less than 60 mL/min
    - c. Hearing loss or neuropathy of any cause Common Terminology Criteria for Adverse Events (CTCAE) Grade  $\geq 2$ .
- Inclusion for Cohort 2
11. Disease progression during or following treatment with at least one platinum-containing regimen (e.g., GC, MVAC, CarboGem, carboplatin-paclitaxel) for inoperable locally advanced or metastatic urothelial carcinoma or disease recurrence, as defined by:
    - a. Regimen is defined as patients receiving at least one cycle of a platinum-containing regimen with response assessment. Patients who received one cycle of a platinum-containing regimen but discontinued due to toxicity are also eligible.

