    - b. Patients who received prior adjuvant/neoadjuvant chemotherapy and progressed within 12 months of treatment with a platinum-containing adjuvant/neoadjuvant regimen are considered as second-line patients.
  12. ECOG (Eastern Cooperative Oncology Group) performance status of  $< 2$
  13. Calculated creatinine clearance (Cockcroft-Gault formula) of  $\geq 20$  mL/min
- Exclusion criteria for ALL subjects
1. Any approved anti-cancer therapy, including chemotherapy, within 3 weeks prior to initiation of trial product; the following exceptions are allowed:
    - a. Palliative radiotherapy for bone metastases or non-target soft tissue lesions completed  $> 7$  days prior to baseline imaging.
    - b. Hormone-replacement therapy or oral contraceptives.
  2. Treatment with any other investigational agent or participation in another clinical trial with therapeutic intent within 28 days prior to Day 1 (first dose of trial product) given that all AEs related to prior treatment have resolved to baseline or Grade 1.
  3. Active central nervous system (CNS) metastases defined as computed tomography (CT) or magnetic resonance imaging (MRI)

evidence of progression and prior radiographic assessments or Leptomeningeal disease.

Subjects that have had prior diagnosis need to have stable disease by having results or performing CT/MRI with 1 month prior to 1st dose of treatment.

4. Uncontrolled tumor-related pain:
  - a. Patients requiring pain medication must be on a stable regimen at trial entry.
  - b. Symptomatic lesions amenable to palliative radiotherapy (e.g., bone metastases or metastases causing nerve impingement) should be treated prior to trial entry.
  - c. Asymptomatic metastatic lesions whose further growth would likely cause functional deficits or intractable pain (e.g., epidural metastasis that is not currently associated with spinal cord compression) could be considered for loco-regional therapy if appropriate prior to first dose of trial product.
5. Uncontrolled pleural effusion, pericardial effusion, or ascites requiring recurrent drainage procedures (once monthly or more frequently)
  - a. Patients with indwelling catheters (e.g., PleurX) are allowed.
6. Uncontrolled hypercalcemia (> 1.5 mmol/L ionized calcium or Ca > 12 mg/dL or corrected serum calcium > ULN) or symptomatic hypercalcemia requiring continued use of bisphosphonate therapy or denosumab:

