Locally advanced or metastatic urothelial cancer cisplatin-ineligible patients for first-line treatment is a new approved FDA and EMA indication for both atezolizumab and pembrolizumab. Atezolizumab approval is based on IMvigor201 Phase 2 trial, a single-arm, multicentric study that included 119 patients evaluable (Balar et al., 2017b). The objective response rate was 23%, including 9% CR. Median DOR was not reached by the time of the publication, range 3.7 to 21+ months, with 70% of responses ongoing as of data cutoff. Responses were observed in all categories of cisplatin ineligibility: 25% in patients with impaired renal function, 25% in PS2 patients and 12% and 14% for patients with hearing loss and peripheral neuropathy respectively. The median OS was 15.9 months and 12-month landmark survival was 75%. AEs grade 3-4 were reported in 16% of patients, led to treatment discontinuation in 34% of patients and led to treatment withdrawal in 8%. IMAEs were reported in 12% of patients and grade 5 in 4 patients. Pembrolizumab approval is based on KEYNOTE-052 Phase 2 trial, a single-arm, multicentric study that included 370 patients evaluable (Balar et al., 2017a). The objective response rate was 24%, including 5% CR. Median DOR was not reached by the time of the publication, with 78% of responses ongoing as of data cutoff. Responses were observed in all categories of cisplatin ineligibility: 27% in patients with impaired renal function, 26% in PS2 patients and 31% for patients with other reasons. AEs grade 3-4 were reported in 16% of patients, 5% leading to treatment discontinuation. In both trials, responses were observed across all categories of PD-L1 expression, with the clinically relevant fact that low or absent PD-L1 does not preclude response.

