4.4.7.5 Bladder Cancer History and Baseline Disease Characteristics

Variables

- Eastern Cooperative Oncology Group (ECOG) Performance Status (0, 1, ≥ 2)
- Time from Initial Diagnosis to First Treatment (years)
- Duration of Primary Curative Intervention (months)
- Disease Free Interval (months)
- Time from Recurrence after a Disease-Free Interval to First Treatment (years)
- Primary Tumor Site (Renal Pelvis, Ureter, Urethra, Urinary Bladder, Other)
- Stage at Diagnosis (I, II, III, IV)
- T Category (T_x, T₀, T_a, T_{is}, T₁, T_{2a}, T_{2b}, T_{3a}, T_{3b}, T_{4a}, T_{4b})
- N Category (N_x, N₀, N₁, N₂, N₃)
- M Category (M₀, M₁)
- PD-L1 tumor proportion score (TPS; < 1%, $\geq 1\% - 10\%$, $\geq 10\%$)
- Current Metastatic Disease Sites (Yes, No)
 - Sites of Current Metastatic Disease: Adrenals, Bone, Bone Marrow, Chest Wall, Central Nervous System/Brain, Fallopian Tubes, Kidney, Large Intestine, Liver, Lung, Lymph Nodes, Pancreas, Peritoneum, Pleura, Rectum, Small Intestine, Spleen, Stomach, Uterus, Other

Analyses

Missing dates for cancer history will be imputed per Section 4.3.2. Frequencies and percentage of subjects will be tabulated for categorical variables by cohort and overall. Percentages will be

based on the total number of subjects in the FAS within each cohort. The following formulas will be used to calculate the above time-specific variables:

Time from Initial Diagnosis to First Treatment = (Date of First Treatment – Date of Initial Diagnosis + 1)/365.25

The following will be included only in subject-level listings:

Duration of primary curative intervention in months = (End Date of Primary Curative Intervention – Start Date of Primary Curative Intervention + 1)/30.4375

Disease-free interval in months = (Date of Recurrence – End Date of Primary Curative Intervention + 1)/30.4375

Time from Recurrence after a Disease-Free Interval to First Treatment in months = (Date of First Treatment – Date of Recurrence + 1)/30.4375

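### Cohort 1 has no ECOG ceiling or creatinine-clearance floor that applies to every subject, because the limits sit inside an either/or list; Cohort 2 states both as stand-alone criteria

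*Protocol*

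**What the plan says.** All eligibility criteria are in Protocol section 1.4; sections 5.2 and 5.3 only refer back to it.

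- **Cohort 1, #10.** The list opens with "Have at least one of the following". Item 10a is "ECOG (Eastern Cooperative Oncology Group) performance status of 2". Item 10b is "Glomerular filtration rate calculated as creatinine clearance (Cockcroft-Gault formula) of" at least 20 and less than 60 mL/min. Item 10c is "Hearing loss or neuropathy of any cause Common Terminology Criteria for Adverse Events (CTCAE) Grade" 2 or higher.
- **Cohort 2, #12 and #13.** These are separate requirements: "ECOG (Eastern Cooperative Oncology Group) performance status of" below 2, and "Calculated creatinine clearance (Cockcroft-Gault formula) of" at least 20 mL/min.
- **All subjects.** Table 1 has hematological, hepatic and coagulation rows but no renal row. No all-subject criterion names an ECOG value.
- **Benchmark.** The Cohort 1 null of 23% comes from the first-line atezolizumab study. Protocol section 2.1 breaks its response rates down by the reason why cisplatin could not be given, as follows: "25% in patients with impaired renal function, 25% in PS2 patients and 12% and 14% for patients with hearing loss and peripheral neuropathy respectively".
- **Reporting.** The baseline variable in SAP 4.4.7.5 begins "Eastern Cooperative Oncology Group (ECOG) Performance Status (0, 1" and ends in an open category of 2 or higher.

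**The concern.** In a list where one item is enough, the values 2 and 20 mL/min define ways in. They do not limit who may come in by another way. The floor of 20 mL/min printed in 10b suggests that a lower renal limit was in mind, yet it has no force for a subject who qualifies by 10a or 10c. Cohort 2, the fitter group, carries both limits unconditionally.

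What is at stake is comparability with a fixed historical rate. Cohort 1 is tested against 0.23 with no concurrent control, so its case mix should resemble the population behind that rate. Section 2.1 describes that population by renal impairment, PS2, hearing loss and neuropathy; ECOG 3-4 is not a named category.

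The endpoint rules give early drop-out a cost. The FAS takes in anyone who received any vaccine (Protocol 9.3, SAP 4.2). Subjects who leave early without a CR or PR count as non-responders (SAP 4.3.3). The primary endpoint is a confirmed response, repeated at least 4 weeks later (Protocol Appendix 4), while scheduled scans fall at Weeks 10 and 22 (Protocol 9.12). A patient with little more than 12 weeks of life expectancy may not reach the second scan.

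**Working it through.** **Step 1. Who can enter Cohort 1 as written.**

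| Patient | Qualifying item | Is there a stand-alone bar in Cohort 1? | In Cohort 2? |
|---|---|---|---|
| ECOG 3-4, clearance 40 mL/min | 10b | None found | Yes, #12 |
| ECOG 3-4, Grade 2 neuropathy | 10c | None found | Yes, #12 |
| ECOG 2, clearance below 20 mL/min | 10a | None found | Yes, #12 and #13 |
| ECOG 0-1, Grade 2 neuropathy, clearance below 20 mL/min | 10c | None found | Yes, #13 |

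ECOG 3-4 alone, or clearance below 20 alone, does not satisfy #10. The gap opens when another item of #10 is met.

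**Step 2. What else might close it.** The other filters are life expectancy of at least 12 weeks (#4), ability to comply (#2), the non-renal values in Table 1, and exclusion 22, which is a judgement about risk. None contains an ECOG or clearance threshold. Protocol section 2.7 names PS2 and renal impairment as reasons for cisplatin ineligibility but sets no outer limit on either.

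**Step 3. Reproduce the plan's own figures.** Inputs from Protocol 1.4 and 9.7.1: 14 subjects in Stage 1, stop at 3 or fewer responses; 33 in total, reject at 13 or more; null 0.23, alternative 0.43.

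P(reject | p) = sum over x = 4 to 14 of b(x; 14, p) × P[Bin(19, p) ≥ 13 − x]

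P(stop at Stage 1 | p) = P[Bin(14, p) ≤ 3]

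- p = 0.23: P(reject) = 0.02437 (stated 0.0244).
- p = 0.43: P(reject) = 0.70266 (stated 0.7027); P(stop) = 0.0839.

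Both stated figures reproduce.

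**Step 4. Illustrate the effect.** The documents give neither the share s of such patients nor their response rate q, so both are assumptions. The others respond at 0.43, and the blended rate is p = (1 − s) × 0.43 + s × q. For s = 10%:

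- q = 0: p = 0.9 × 0.43 = 0.387
- q = 0.215 (half): p = 0.387 + 0.1 × 0.215 = 0.4085
- q = 0.43 (equal): p = 0.43

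Each cell gives power / probability of stopping at Stage 1:

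| Share s | q = 0 | q = 0.215 | q = 0.43 |
|---|---|---|---|
| 5% | 0.613 / 11.2% | 0.659 / 9.7% | 0.703 / 8.4% |
| 10% | 0.515 / 14.6% | 0.613 / 11.2% | 0.703 / 8.4% |
| 20% | 0.318 / 23.5% | 0.515 / 14.6% | 0.703 / 8.4% |

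**Step 5. Direction.** If the treatment adds nothing and 10% of subjects never respond, the blended rate is 0.9 × 0.23 = 0.207 and P(reject) falls from 0.0244 to 0.0103. If these patients respond less well, the error is toward stopping or failing, not toward false success.

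**The case against.** The strongest reply concerns consequence, since the literal reading of #10 is hard to dispute.

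- **Benchmark.** A reader might infer that the historical study excluded both groups. The documents do not show this. Section 2.1 gives categories in which responses were seen, not eligibility limits, and its renal category has no stated floor. All that stands is that ECOG 3-4 is not a named category.
- **Response by frailty.** The rates in section 2.1 do not fall for the two main categories: 25% for renal impairment and 25% for PS2 against 23% overall, and 27% and 26% against 24% in the pembrolizumab study. The prognostic role of ECOG above 0 in the same section comes from second-line vinflunine data and does not separate ECOG 2 from 3-4. This is a fair reason not to treat zero response as an estimate. It does not speak to ECOG 3-4 directly.
- **Other filters.** Albumin and hemoglobin minima, and the exclusions for uncontrolled pain, recurrent effusions and NYHA Class II or greater, will also keep out many very frail patients. A share of 10% to 20% may well be too high. These filters reduce the number of such patients without supplying the missing limits.
- **SAP category.** It might be inferred that ECOG 3-4 subjects would be hidden. The summary table would pool them with ECOG 2, but SAP 4.4.1 lists all individual data, so they would be visible there. This part is minor.
- **Safety.** A reader might call this a demonstrated safety gap. No passage ties the safety of either product to an ECOG or clearance threshold, so that is not claimed.

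**Conclusion.** The point holds as a defect in the entry rule. Followed literally, criterion 10 admits to Cohort 1 ECOG 3-4 patients, and patients with clearance below the 20 mL/min printed in 10b, provided they meet another item of the list. Cohort 2 bars both groups.

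The sample-size figures are right and need no change. The effect on power cannot be estimated from the documents. At an assumed 10% share it runs from no loss (0.703) through 0.613 to 0.515, depending on whether these patients respond like the others, half as often, or never. The zero-response figures are the worst case for each share. Any bias is toward futility, so the risk is losing a useful signal in a cohort that starts with only 70% power.

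**What to change.** Reconcile #10 with #12 and #13. State the ECOG upper limit and the creatinine-clearance lower limit for Cohort 1 as stand-alone criteria that apply whichever part of #10 qualifies the subject. The sponsor should confirm whether the values already printed in 10a and 10b are meant to be those limits; this review does not choose them. Then align the ECOG category in SAP 4.4.7.5: if ECOG is capped at the 10a value, the open top category can be labelled with that single value; if higher values are intended to be eligible, they should be shown separately.

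The cost is two lines in the protocol and one label in the SAP, with the usual IRB review of an amendment. The sample size and decision rules do not change. The downside is that a few very frail or severely renally impaired patients may become ineligible.

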### 1.5 Trial Procedure Schedule

Trial Procedure	Screening Phase Day -28 to Day 1	Week (3 wk interval +/- 4 days)						Week (6 wk interval +/- 1 wk)		Week (12 wk interval +/- 2 wks)						Long Term FU	
		1	4	7	10	13	16	22	28	40	52	64	76	88	100 EOT 	3-month interval +/- 2 wks	
		Day															
		1	22	43	64	85	106	148	190	274	358	442	526	610	694 EOT		
		Visit															
		1	2	3	4	5	6	7	8	9	10	11	12	13	14		
Trial Procedures																	
Informed Consent 	X																
Demographics	X																
Medical History	X																
Physical Exam incl. vital signs 	X																
Targeted PE incl. vital signs 		X	X	X	X	X	X	X	X	X	X	X	X	X	X	X	
ECOG	X	X	X	X	X	X	X	X	X	X	X	X	X	X	X	X	
ECG 	X																
Eligibility Criteria	X																
Concomitant Medications	X	collected at all clinic visits (including atezolizumab dosing visits)															
Adverse Events 	X	collected at all clinic visits (including atezolizumab dosing visits)														X 	
Survival Status and Auto-immune/ IM clinical manifestation																X	
Tumor Biopsy	X 			X 													
Radiology Assessments																	
CT scan: Thorax, Abdomen and Pelvis 	X				X			X	X	X	X	X	X	X	X	X	

Trial Procedure	Screening Phase Day -28 to Day 1	Week (3 wk interval +/- 4 days)						Week (6 wk interval +/- 1 wk)		Week (12 wk interval +/- 2 wks)						Long Term FU	
		1	4	7	10	13	16	22	28	40	52	64	76	88	100 EOT 	3-month interval +/- 2 wks	
		Day															
		1	22	43	64	85	106	148	190	274	358	442	526	610	694 EOT		
		Visit															
		1	2	3	4	5	6	7	8	9	10	11	12	13	14		
Laboratory Assessments																	
Hematology 	X	X	X	X	X	X	X	X	X	X	X	X	X	X	X	X	
Serum Chemistry 	X	X	X	X	X	X	X	X	X	X	X	X	X	X	X	X	
HIV, HbsAg, HCV	X																
INR, PT, aPTT	X																
Thyroid function test	X	X		X		X											
Biomarker Analyses 	X		X		X			X			X						
Urinalysis	X		X		X		X	X	X	X	X	X	X	X	X	X	
Pregnancy Test 	X	X	X	X	X	X	X	X	X	X	X	X	X	X	X	X	
Dosing																	
Prime Vaccine: MVA-BN-CV301 		X	X														
Boost Vaccine: FPV-CV301 				X	X	X	X	X	X	X	X	X	X	X	X	X	
Atezolizumab		X	X	X	X	X	X										

EOT = End of Treatment, PE = Physical Examination, AE = Adverse Event, SAE = Serious Adverse Event, AESI = Adverse Event of Special Interest, WOCBP = Women of Childbearing Potential

 ICF can be obtained prior to Screening visit

 Blood pressure and pulse rate should be obtained after the subject has been seated in an upright position for at least 5 minutes.

 Troponin I will only be measured if clinically indicated.

 The reporting period for non-serious AEs and unrelated SAEs/AESIs ends 30 days after last administration of the trial product. The reporting period for related SAEs/AESIs ends 100 days after last administration of the trial product. A phone follow-up will be performed 100 days after the last administration of trial product to collect this information and schedule a follow-up visit, if clinically indicated.

 Patients who do not have archived tissue specimens meeting eligibility requirements must undergo a biopsy sample collection during the screening period. Acceptable samples included core needle biopsies for deep tumor tissue (minimum three cores) or excisional, incisional, punch, or forceps biopsy samples for cutaneous, subcutaneous, or mucosal lesions.

 Optional at any of the following visits: Visit 3-6.

 If there is a medical reason, subject may have MRI instead of CT scan upon approval from BN.

 Hematology and Serum Chemistry will be performed prior to every atezolizumab infusion. Hematology will include hemoglobin, hematocrit, red blood cell count, total white blood cell count with differential, platelet count, mean cell volume, mean corpuscular hemoglobin, and red blood cell distribution width. Serum chemistry will include: total protein, albumin, alkaline phosphatase, total bilirubin, ALT, AST, lactate dehydrogenase, creatinine, blood urea nitrogen, uric acid, glucose, calcium, phosphorus, bicarbonate, chloride, potassium, sodium, lipase and amylase.

 Sample collection (peripheral blood for PBMC, serum) must occur prior to vaccine dosing. Sample collection for Biomarker analyses should be repeated if subject comes off trial due to PD or AE or if the subject has an objective response.

 For WOCBP, a pregnancy test is required prior to every atezolizumab infusion. Urine or serum pregnancy test is acceptable at any given visit depending on investigator and/or patient preference.

 The trial subject must be kept under close observation at the clinical trial site for at least 30 minutes following vaccinations.

 EOT visit should take place within 28 days of withdrawal.

## 2 Background Information and Scientific Rationale

### 2.1 Introduction

The estimated incidence of urothelial cancers -including bladder, ureter and renal pelvis- for 2017 in the US is 146,650 cases. The mortality estimated for urinary system cancers is 32,190 deaths (Siegel et al., 2017). Approximately 5% of newly diagnosed bladder cancers present with metastatic disease and 30% with muscle-invasive bladder cancer. Roughly 50% of patients with muscle-invasive bladder cancer will develop distant metastasis (Milowsky et al., 2016). The median age of diagnosis of bladder cancer patients is 73 years, with more than 70% older than 65 years (Miller et al., 2016).

Before the Food and Drug Administration (FDA) approval of programmed death-1 (PD-1)/programmed death ligand-1 (PD-L1) inhibitory antibodies in 2016 and 2017, chemotherapy was the only treatment available for locally advanced or metastatic urothelial bladder cancer. The most efficacious chemotherapy regimens are those containing cisplatin, which represents a challenge for frail and unfit patients. Low performance status, advanced age, compromised renal function and comorbidities limit the capability of these patients to cope with intensive platinum-based regimens. A first step in selecting the proper treatment for UC patients is to identify to which category they belong, cisplatin eligible or ineligible. The category of cisplatin eligible patients is especially relevant for first-line treatment, since the administration of standard regimens such as DDMVAC [dose-dense methotrexate, vinblastine, doxorubicin and cisplatin] or cisplatin/gemcitabine is associated with a fraction of long-term survivors. However, the prognosis is dismal for patients with disease progression after first-line chemotherapy. The ORR was lower than 10% for all the single agents tested. No chemotherapy agent was ever approved by the FDA for second-line treatment and only vinflunine achieved the approval by the European Medicines Agency (EMA), based on a modest 2-month and non-statistically significant prolongation of OS in a randomized Phase 3 clinical trial (Balar et al., 2017a), (Bellmunt et al., 2009). A prognostic model was derived from the vinflunine pivotal trial database in which the most important prognostic factors were ECOG Performance status higher than 0, hemoglobin level less than 10 g/dL and liver metastasis (Bellmunt et al., 2010). Time from prior chemotherapy was later identified as an additional independent prognostic factor and accordingly it was recommended as a stratifying factor in randomized clinical trials (Sonpavde et al., 2013). In a poster communication to the (ASCO) Annual Meeting 2014 (Sonpavde, 2014), twelve Phase 2 clinical trials studying single agents or combinations included 711 patients and the global median OS was 6.8 months, 95% C.I. 6.2 to 7.3 months, with a range of 3.9 to 10.8 months. The median OS reported in the Phase 3 clinical trial that compared vinflunine versus investigator's chemotherapy choice were 6.9 and 4.6 months respectively (Balar et al., 2017a), (Bellmunt et al., 2009).

As of December 2017, the FDA has approved five PD-1/PD-L1 inhibitory antibodies for locally advanced (LA) or metastatic (M) UC. A summary of these drugs and labels is presented in the following table (Table 2).

